### **7.3.3 *Medical History and Prior Medication***

Medical history and prior medication information before the first study medication will be summarized by treatment group using relative frequencies. Listings of medical history and prior medication will be presented. The results will be based on the MITT analysis population.

## **7.4 *Extent of Exposure***

### **7.4.1 *Study Therapy***

In general, extent of exposure during ST will be summarized for the As-treated analysis population in two ways:

- by the number of study drug injections: Frequency distribution of number of injections will be summarized
- by the number of days: the subject is known to be on study drug, ignoring any dosing interruptions

In general, exposure to study drug during the short-term period (ST) is calculated as follows:

1. The subjects who enter in the long-term extension period (LTE) within 7 days of the last study medication in ST,

Exposure (in days) = (date of first study medication in LTE - date of first study medication in ST).

2. All other subjects (including the subjects who discontinue early, complete the ST but do not enter in the LTE or enter LTE after 7 days post the last dose of the ST):

Exposure (in days) = date of last study medication in ST - date of first study medication in ST + 7

Note that, the offset of 7 days represents the dosing interval of 7 days.

The frequency will be presented according to the duration ranges (in days) : <=28, 29-56, 57-84 and so on.

#### **7.4.2 Discontinuations from Study Therapy**

Discontinuation from study therapy is defined as subject's termination of the study medication without resumption prior to study completion. Note that, subjects are to be discontinued if more than 3 consecutive doses of study medication are missed. Discontinuation from study therapy during the ST period will be summarized by reason for the premature termination, taken from the study status case report form (CRF) pages. These summaries will be provided based on the MITT analysis population by randomized treatment group and overall.

#### **7.4.3 Treatment Compliance**

The CRF for this study will capture information on injections of the study medication. All subjects who skip any study drug injection will be listed. The number of subjects with missed injections (excluding missed injections due to premature discontinuation from the study) by number of missed injections will be summarized based on the As-treated analysis population for the ST period by treatment groups.

#### **7.4.5 Immunosuppressant Medication**

For the purpose of this analysis plan, the term DMARDs will refer to non-biologic DMARDs. Immunosuppressant medications summaries will be provided to present the medication use of corticosteroids, NSAIDs, and DMARDs. Number and percent of subjects receiving corticosteroids, NSAIDs, and DMARDs will be summarized by treatment group for MITT analysis population during the ST period.

A comprehensive listing of all concomitant medications including immunosuppressant will be also provided for the MITT analysis population.

#### **7.4.6 Corticosteroids**

The average daily corticosteroid dose (prednisone equivalent) and its change from baseline will be summarized over time by treatment group for the ST period.

### **7.5 Efficacy**

The efficacy analyses will be performed using the efficacy analysis population. The results will be grouped by "as randomized" treatment groups, unless otherwise specified. No formal statistical testing was pre-specified for other efficacy endpoints except the primary endpoint of BICLA response at Day 169. The analyses of binary endpoints and continuous endpoints will be provided over time including the milestone visits (e.g. Day 85, Day 169 etc.).

### **7.5.1 Primary Efficacy Endpoints in the Short-term Period**

The primary efficacy endpoint is BICLA response rate at Day 169.

The Chi-square tests will be used to compare the BICLA response rates at Day 169 between each of the active treatment arms and the placebo arm. The Chi-square p-value will be provided for each comparison between the active treatment and the placebo arm. No adjustment will be made for multiplicity. In addition, the difference of the response rates between each active treatment and the placebo will be estimated and their corresponding 90% confidence interval will be calculated for Day 169 visit and other applicable visits.

The point estimate for BICLA response rate along with 90% confidence interval will be calculated for each treatment arm for each applicable visit.

All subjects who prematurely discontinue the trial after receiving study medication will have missing data imputed as non-responder at all scheduled protocol visits subsequent to the point of discontinuation. The analysis will be performed based on Efficacy Analysis Population. More details of imputation rule for classification of binary response status are provided in [Sections 8.3, 8.1.1, and 8.1.2](#).

For BICLA, the number of responders, together with the rescue status (with or without one-time rescue allowed per protocol) will be summarized by treatment group. At the same time, the number of nonresponders will be summarized by treatment group, together with the reasons for nonresponse.

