iii) Subjects must have at least one of the following manifestations of SLE, as defined by the BILAG criteria as modified for use in this study, which must be confirmed by the External Adjudication Committee:

(1) BILAG A or B score in the Mucocutaneous body system

(2) BILAG A or B score in the Musculoskeletal body system due to active polyarthritis defined as follows:

(a) “BILAG A”: severe arthritis (BILAG #41) manifested by observed active synovitis in ≥ 2 joints with marked loss of functional range of movements and significant impairment of basic activities of daily living, that has been present on several days cumulatively over the past 4 weeks, including at the time of the screening visit. Basic ADLs are defined as the following activities which require assistance or assistive devices (at least one must be present and documented in source): ambulation, toileting, grooming including bathing, dressing, feeding oneself (not responsive to steroids up to 10 mg/day, antimalarials, NSAIDs).

(b) “BILAG B”: Moderate arthritis or tendonitis or tenosynovitis (BILAG #42) defined as tendonitis/tenosynovitis or active synovitis in ≥ 1 joint (observed or through history) with some loss of functional range of movements which lead to some loss of functional range of motion as manifested by effects on instrumental ADLs (such as cooking, driving, using the telephone or computer, shopping, cleaning, etc.) which has been present on several days over the last 4 weeks and is present at the time of the screening visit.

(3) if only one “B” and no “A” score is present in the Mucocutaneous body system or in the Musculoskeletal body system due to arthritis, then at least one B must be present in the other body systems for a total of 2 “B” BILAG body system scores.

iv) Unless intolerant, subjects must be currently receiving at least one of the following steroid-sparing agents for a minimum of 12 weeks, and at stable dose for at least 8 weeks (56 days) prior to signing consent:

Azathioprine (AZA), chloroquine, hydroxychloroquine, methotrexate (MTX), leflunomide, mycophenolate mofetil/mycophenolic acid*. Subjects must remain on stable dose throughout the study[#].

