#### 5 SAMPLE SIZE AND POWER

The sample size calculation is based on power to compare the proportion of subjects who achieve BICLA response (the BICLA response rate) at Day 169 between each BMS-931699 dose arm and the placebo arm. With a one-sided continuity corrected chi-squared test at significance level 0.05, data from 70 treated subjects per arm will provide at least 89% power to detect a 25% increase in the BICLA response rate in the active treatment arm (i.e.. 50% response rate in BMS active arm) compared to placebo and provide 74% power to detect 20% increase in the BICLA response rate in the active treatment arm (i.e., 45% response rate in BMS-931699 arm) compared to placebo, assuming that the placebo arm has 25% response rate which is reasonable based on the EMBLEM phase 2 trial result. No adjustment will be made for multiplicity.

The primary efficacy analysis will be conducted on all randomized patients who received at least one dose of the study drug. In order to get 70 treated subjects per arm, an adequate numbers of subjects need to meet the inclusion/exclusion criteria at screening.

If the interim analysis for futility and dose adaptation suggests an additional dose arm at a lower dose level needs to be added, then up to 40 additional subjects may be randomized.

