### **7.3.2 Demography and Baseline Characteristics**

Demographic and baseline disease characteristics will be summarized by randomized treatment group and overall based on the MITT analysis populations. For continuous variables, they will be summarized using means, standard deviations and ranges. The distribution of categorical variables such as gender, race etc. will be summarized by treatment group using frequency and percentage.

Demographic characteristics include the following:

- Age in years
- Weight in kg
- Gender: Male, Female
- Race
- Ethnicity (Hispanic and Non-Hispanic)
- Region (North America, South America, Europe and Asia)
- Stratification [Japan vs. Non-Japan, MMF use (Y/N)]
- 

Baseline clinical characteristics include the following:

- Time from First Diagnosis of SLE (years)
- Tender Joint Counts
- Swollen Joint Counts

- Active (Both Tender and Swollen) Joint Counts
- BILAG classifications and numerical scores
- SLEDAI-2K Score
- CLASI Score
- Physician's global assessment of disease activity (MDGA)
- Subject's global assessment of disease activity (PGA)
- SLICC/ACR damage index
- Total corticosteroid daily dose (prednisone equivalent) at baseline

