## **8 CONVENTIONS**

### **8.1 Calculations of Key Measures**

#### **8.1.1 Evaluation of BICLA response**

BICLA response is defined based on the following components:

- British Isle Lupus Assessment Group improvement, defined as BILAG ‘A’s at Baseline improved to ‘B’/‘C’/‘D’, and BILAG ‘B’s at baseline improved to ‘C’/‘D’, and no BILAG worsening in other BILAG organ systems such that there are no new BILAG ‘A’s or greater than 1 new BILAG ‘B’; and,
- No worsening in the SLEDAI-2K total score compared to Baseline (defined as no increase in SLEDAI total score); and,
- No worsening in the physician’s global assessment (MDGA) of disease activity (“no worsening” is defined as less than 10% worsening, equivalent to a 10mm increase on a 100mm visual analog scale [VAS]) compared to Baseline; and,
- No changes in concomitant medications according to the following criteria:
  - No increase of or addition of a new immunosuppressant agent (azathioprine, methotrexate, anti-malarial) over baseline levels

- No increase in corticosteroid dose above baseline level outside of those allowed per protocol.

If a subject failed any of the above criteria above, the BICLA response status of the subjects will be set to non-responder.

For the determination of missing BICLA response status, all subjects who prematurely discontinue from the study medication will be imputed as non-responder at all scheduled efficacy visits subsequent to the point of discontinuation.

If any subject has at most one missing component (e.g. MDGA for BICLA) at a given efficacy visit not due to premature discontinuation, the component-wise response status will be imputed based on the following rules.

- If the given visit is not the last scheduled efficacy visit (Day 169), imputation will depend on the observed responses from the immediate previous efficacy visit and the immediate next efficacy visit within 28 days of the current visit date.
- If the given visit is the last scheduled efficacy visit (Day 169), the imputation will depend on the observed responses at the previous 2 consecutive efficacy visits (within 56 days).
- If a subject has response (at component level) at both efficacy visits, the missing response status at current visit will be imputed as responder. Otherwise, response status will be set to non-responder.

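### The primary BICLA test is valid but uses no baseline disease-activity covariate; pre-specifying adjustment for data already collected would probably gain a little precision at low cost

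*SAP*

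**What the plan says.** **Primary analysis.** SAP 7.5.1: "The Chi-square tests will be used to compare the BICLA response rates at Day 169 between each of the active treatment arms". Each is compared with placebo. SAP Table 7.1-1 adds a one-sided p-value and a 90% CI for the treatment difference. The protocol synopsis and Protocol 8.5.2 give the same chi-square analysis. BICLA at Day 169 is the only endpoint formally tested (SAP 7.5).

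**Adjustment.** SAP 7.5.4 plans a CMH sensitivity analysis by randomisation strata, which SAP 7.3.2 lists as Japan v non-Japan and MMF use. For continuous secondary endpoints, SAP 7.5.2 allows a baseline covariate if necessary. Nothing comparable is offered for BICLA.

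**Baseline data.** SAP 7.3.2 tabulates "BILAG classifications and numerical scores", SLEDAI-2K, MDGA and steroid dose. Protocol Table 5.1-2 schedules BILAG, SLEDAI-2K and MDGA on Day 1.

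**Endpoint.** SAP 8.1.1 has the BILAG component "defined as BILAG ‘A’s at Baseline improved to ‘B’/‘C’/‘D’, and BILAG ‘B’s at baseline improved to ‘C’/‘D", with further conditions on new BILAG activity, SLEDAI-2K, MDGA and medication.

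**Entry.** Protocol 3.3.1 admits a subject with one A in the mucocutaneous or musculoskeletal system. With a single B there and no A, "then at least one B must be present in the other body systems for a total of 2 “B” BILAG body system scores". No upper limit on the number of active systems is stated there.

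**Power.** SAP 5 sets the test: "With a one-sided continuity corrected chi-squared test at significance level 0.05". For the larger effect it says "data from 70 treated subjects per arm will provide at least 89% power to detect a 25% increase". For the smaller effect the same sample is said to "provide 74% power to detect 20% increase in the BICLA response rate in the active treatment arm". Both figures are computed "assuming that the placebo arm has 25% response rate".

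**The concern.** Subjects start with different numbers of A/B systems, and the BILAG component requires those systems to improve. A subject with three to improve plausibly has a lower chance of response than a subject with one. If so, part of the between-subject variation in BICLA is predictable at baseline, and an unadjusted comparison leaves it in the error term.

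Randomisation is not stratified on disease activity, so arms of 70 will differ by chance in baseline burden. All four dose comparisons share one placebo arm, so an unlucky placebo draw would shift all four estimates the same way. At stake is some power at the smaller planned effect and some width in the intervals used to compare doses.

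**Working it through.** **1. Reproduce the stated power.** Inputs from SAP 5: n = 70 per arm, one-sided 0.05, placebo 25%, active 50% or 45%, continuity-corrected. With difference d, the correction replaces n by m = (n − 1/d)²/n. Power = Φ[(d√m − 1.645√(2p̄(1−p̄))) / √(p0(1−p0) + p1(1−p1))].

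- 50% v 25%: m = 66²/70 = 62.2; (0.25×7.889 − 1.645×0.6847)/0.6614 = 1.279; power 90.0%.
- 45% v 25%: m = 65²/70 = 60.4; (0.20×7.769 − 1.645×0.6745)/0.6595 = 0.673; power 75.0%.

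Exact binomial power of the corrected test is 89.8% and 74.7%. The plan's 89% and 74% hold.

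**2. Fix the scale.** With m = 70 (no correction) the same formula gives 92.8% and 80.4%. With unpooled variance, SE = √((0.2475 + 0.1875)/70) = 0.0788 and power at 45% v 25% is Φ(0.20/0.0788 − 1.645) = 81.4%. The step from 74% to 80-81% is therefore the continuity correction. Gains from adjustment must be counted from 80-81%.

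**3. Gain for an assumed prognostic strength.** R² is the share of response variance explained by baseline. The documents do not give it. Adjustment multiplies the variance by (1 − R²), which is equivalent to n/(1 − R²) subjects per arm. At 45% v 25%:

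| R² (assumed, both arms) | Effective n per arm | Power, unpooled | Power, pooled | 90% CI half-width (points) |
|---|---|---|---|---|
| 0 | 70.0 | 81.4% | 80.4% | 13.0 |
| 0.02 | 71.4 | 82.1% | 81.1% | 12.8 |
| 0.05 | 73.7 | 83.1% | 82.1% | 12.6 |
| 0.10 | 77.8 | 84.8% | 83.9% | 12.3 |
| 0.13 | 80.5 | 85.9% | 85.0% | 12.1 |

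**4. What R² is plausible for the A/B count?** Suppose each of k systems improves independently with probability q, so P(response) = q^k, and solve q for 25% and 45% overall.

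- Assumed shares 15/55/22/8% for k = 1 to 4: q = 0.505 and 0.686; R² = 0.084 (placebo) and 0.066 (active); power 83.9%.
- Assumed shares 30/45/20/5%: q = 0.454 and 0.651; R² = 0.109 and 0.090; power 84.8%.

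Over a wider set of assumed shares, R² was 0.07-0.13 on placebo and 0.06-0.11 on active. At the upper end, SE = √((0.1875×0.87 + 0.2475×0.89)/70) = 0.0740 and power is about 85.5%, a gain of about 4 points. The table's last row is slightly higher because it puts 0.13 in both arms.

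**5. Simulation with weaker links.** This used 20,000 replicates at 45% v 25%, a logistic slope per extra system, and the same two sets of shares. It compared uncorrected chi-square with CMH stratified by count.

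| R² on placebo | Chi-square | CMH by count | Change (points) |
|---|---|---|---|
| 0 | 80.2%, 80.2% | 79.6%, 79.7% | −0.6, −0.5 |
| 0.010, 0.011 | 80.5%, 80.2% | 80.4%, 80.2% | −0.1, 0 |
| 0.026, 0.028 | 80.3%, 80.6% | 81.1%, 81.3% | +0.8, +0.7 |
| 0.054, 0.058 | 80.4%, 80.3% | 82.2%, 82.4% | +1.8, +2.1 |
| 0.087, 0.094 | 80.6%, 80.5% | 83.7%, 84.3% | +3.1, +3.8 |

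Break-even is near R² = 0.01. The last row corresponds to placebo response roughly halving with each extra system. A separate simulation of a standardised risk difference, with the count and two non-prognostic covariates, gave power of 80.9% to 84.6% and type I error near 5%.

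**6. Chance imbalance.** The SD of the shift in the crude difference attributable to baseline is SE × √R²: 7.88×√0.05 = 1.8 points, or 7.88×√0.10 = 2.5 points.

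**The case against.** **The plan contains no error.** This stands. The chi-square is valid, is specified the same way in protocol and SAP, and matches the sample-size basis. A reader might infer that chance imbalance biases the result. It does not: it is random error, already covered by the test and the 90% CI. Adjustment only makes that error smaller.

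**The count need not be prognostic.** This stands in part. An A need only reach B, while a B must reach C or D, so systems are not equal hurdles. A subject who enters with one A may also have Bs. The entry rule applies at screening, whereas baseline is normally Day 1 (SAP 8.2), so the distribution of the count is unknown. Non-response also comes from discontinuation, medication changes, and worsening of SLEDAI-2K or MDGA. All this weakens the link and is why the case rests on low R² values. It does not remove the reason to expect a link.

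**SLEDAI-2K and MDGA may not help.** A reader might infer that they would add to the gain. The documents do not support this. Both enter BICLA only as no worsening, and a higher baseline could make worsening less likely, which would work against the effect of the count.

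**Other analyses may use covariates.** Protocol 5.5.1 allows clinical covariates to be explored in exposure-response work, and parts of SAP 7.11 are redacted. The point is therefore limited to the planned primary and sensitivity analyses of BICLA.

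**Changing the primary test reaches beyond SAP 7.5.1.** This stands and is taken up in the fix.

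**Conclusion.** The point holds as a modest, optional improvement in efficiency. No disease-activity covariate enters the planned primary or sensitivity analyses of the one tested endpoint, although relevant baseline data are collected and the endpoint's definition gives a reason to expect them to matter.

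If the A/B count explains about 0.02-0.13 of response variance, the gain at 45% v 25% is about 1 to 4 power points from 80-81%, and the 90% CI half-width falls from 13.0 to 12.1-12.8 points. If the count predicts nothing, about half a point is lost, so the precision is inexpensive but not free. R² and the distribution of the count are assumptions; only the direction can be argued from the documents.

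A reader might infer that adjustment could lift power from 74% to about 90%. That mixes a continuity-corrected figure with an uncorrected one. It also needs a correlation of 0.5 (R² = 0.25), for which the documents give no support.

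**What to change.** Before unblinding:

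1. In SAP 7.5.1, make the primary estimate a standardised (marginal) risk difference from a logistic model. The terms are treatment, number of baseline BILAG A/B systems, baseline SLEDAI-2K, baseline MDGA and the randomisation strata. Report a robust 90% CI and a one-sided p-value for each dose v placebo. State how the count enters, since high counts may be sparse.
2. Keep the unadjusted chi-square and crude difference as the supporting analysis.
3. Put matching wording in the protocol synopsis and Protocol 8.5.2, so that protocol and SAP do not name different primary analyses.
4. In SAP 7.10.2 and the Interim Analysis SAP, state which test defines success for the predictive probability. The 0.2 futility threshold was set by simulation, so confirm that it still behaves as intended if the test changes.

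The target quantity (a difference in response rates), the Efficacy Analysis Population and the non-responder imputation stay as they are.

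**Cost.** No new data; modest programming; a primary result that cannot be read from a 2×2 table; alignment of the protocol and the Interim Analysis SAP. If the sponsor prefers to keep the chi-square as primary, the same model could be pre-specified in SAP 7.5.4 beside the CMH analysis. That avoids items 3 and 4 and keeps part of the value.

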### **7.5.2 Secondary Efficacy Endpoints in the Short-term Period**

For each of the binary endpoints (SRI(X) etc.), the estimate and its corresponding 90% confidence interval will be calculated for the difference of the proportions between each active treatment arm and the placebo arm for each applicable visit, similar to the primary analysis except no p-values will be provided.

For each of the continuous endpoints (BILAG-2004, SLEDAI, MDGA, CLASI, etc.), the mixed model will be fit with treatment, visit, and treatment-by-visit interaction as the fixed effects and measurements within each subject as the repeated measurements. The baseline value will be added into the model as a covariate if necessary. Based on the mixed model, the estimate and 90% confidence interval will be calculated for the difference between each active treatment and the placebo at each specified visit. No p-values will be provided. In addition, Descriptive summary statistics of mean change from baseline and 90% confidence interval for each treatment arm will be provided. The missing data in continuous measures will be handled via utilization of mixed model procedure in SAS.

### **7.5.3 Subgroup Analyses**

The subgroup analyses of the primary and selected secondary endpoints ((SRI (X): X = 4, 6.)) will be performed within the following predefined subgroup (Non-Japan subjects). If the value of

the grouping variable cannot be determined for a subject, the subject will be excluded from the corresponding subgroup analysis.

In addition, other subgroup analyses may be performed on primary and selected secondary endpoints as post-hoc analysis.

#### **7.5.4      *Sensitivity Analyses***

Sensitivity analysis for the primary endpoint: Adjustment for the randomization strata using Cochran-Mantel-Haenszel (CMH) methods will be applied on the primary endpoint.

If at least 15-20% of total subjects through all treatment arms in the efficacy analysis population discontinued due to any reasons other than Lack of Efficacy (LOE), AE or Unknown reason, a sensitivity analysis may be performed. The subjects who have missing response due to premature discontinuation with reasons other than LOE, AE or Unknown will be excluded from the analyses, hence defining the sensitivity analysis population. The sensitivity analysis will be carried out for the primary and selected secondary endpoints (SRI (X): X = 4, 6.) based on the sensitivity analysis population.

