## **2.2 Treatment Assignment**

After completion of all screening evaluations and confirmation of eligibility, subjects will be randomized on Day 1 to one of the following dosing arms in a 1:1:1:1:1 ratio in Part 1 of the study design: BMS-931699 at 12.5mg weekly sub-cutaneous (SC) injection, BMS-931699 at 12.5mg every other week (EOW) SC injection, BMS-931699 at 5mg EOW SC injection, BMS-931699 at 1.25mg EOW SC injection, or Placebo SC injection. The randomization ratio and the treatment arms may be modified based on the results from the two interim analyses defined in [Section 7.6](#).

In this study, subjects will be randomized to receive one of the treatments according to a computer-generated randomization scheme prepared by a Randomization Coordinator within the Drug Supply Management Department of BMS Research and Development.

During the Screening visit, the investigative site will call into the enrollment option of the Interactive Voice Response System (IVRS) designated by BMS for assignment of a 5-digit subject number that will be unique across all sites. Enrolled subjects, including those not dosed, will be assigned sequential subject numbers starting with 00001, 00002, 00003.... 00010. The patient identification number (PID) will ultimately be comprised of the site number and subject number. For example, the first subject screened (i.e., enrolled) at site number 1, will have a PID of 0001 00001. Once it is determined that the subject meets the eligibility criteria following the Screening visit, the investigative site will call the IVRS to randomize the subject into the treatment period.

Every randomized subject will be required to come to the clinic/research center weekly to be dosed. This will ensure double-blind is maintained despite the variability of regimens. Subjects randomized to weekly subcutaneous injections of either placebo or BMS-931699 will be dosed weekly as per schedule and subjects randomized to one of the every other week arm will be alternating between receiving a subcutaneous injection of BMS-931699 one week and one of placebo the following week.

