**Table 7.1-1: Planned Efficacy Analyses**

Measure of Interest (Primary and Secondary Efficacy Endpoints):	Analysis Method
Primary endpoint (Binary): BICLA response rate at Day 169	Chi-Square test, one sided p-value will be provided. Point estimates and 90% CI of treatment difference. No multiplicity adjustments.
Binary endpoints : SRI(X) [ X= 4, 5, 6, 8] at Day 85 and Day 169, BICLA response rate at Day 85, CLASI Response at Day 85 and Day 169	Point estimate and 90% CI of response rate, point estimates and 90% CI of treatment difference
Continuous endpoints: CLASI, BILAG-2004, SLEDAI-2K, MDGA, ACR 28 [tender, swollen, and active, (i.e. joints that are both tender and swollen) joint	Mixed model analysis, point estimates and 90% CI for mean change from baseline within treatment groups, point estimates and 90% CI for mean change from baseline between treatment groups (BMS vs. PLA)

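### The one dropout sensitivity analysis for Day 169 BICLA is optional, has a range as its trigger, and deletes treated subjects by reason for leaving, so it cannot show that the primary result is robust

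*SAP*

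**What the plan says.** Protocol 8.1 and SAP 7.5.1, 8.1.1 and 8.3 treat premature discontinuation as non-response for BICLA, and protocol 8.1 makes no sample size allowance for it.

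SAP 7.5.4 lists two sensitivity analyses of the primary endpoint. The first is a Cochran-Mantel-Haenszel analysis adjusted for the randomisation strata, which has no bearing on dropout. The second concerns subjects who left for a reason other than lack of efficacy (LOE), adverse event (AE) or unknown; I call them other-reason leavers. Its trigger begins "If at least 15-20% of total subjects through all treatment arms". Once the trigger is met, the analysis is permitted, not required. Its rule is "The subjects who have missing response due to premature discontinuation with reasons other than LOE, AE or Unknown will be excluded from the analyses". Subjects who left for LOE, AE or unknown reasons stay in as failures.

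Two further analyses touch on discontinuation without testing this assumption. The per-protocol analysis (SAP 7.5.5) is based on eligibility and dosing deviations. Time to treatment failure (SAP 7.11.2) counts discontinuation as an event, but it is a different endpoint. No readable section keeps every treated subject and varies what is assumed about the leavers' BICLA status. SAP 7.11.1 and 7.11.3 are withheld from the public copy and could not be checked.

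**The concern.** Membership of the sensitivity population depends on something that happens after randomisation, and on a reason recorded on the CRF status pages. Protocol 3.5 lists causes of discontinuation, such as the subject's request, failure to comply, or new lupus manifestations needing non-protocol medication. The readable text does not say these must be recorded as lack of efficacy. Some other-reason leavers may therefore have left because their disease was poorly controlled. If so, and if the numbers differ between arms, removing them from the denominator shifts the comparison.

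The trigger adds two difficulties. A range is not a threshold: at 17% pooled, running the analysis and not running it both comply with the SAP. A pooled percentage also takes no account of imbalance between arms, which is the condition under which dropout matters most.

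What is at stake is how far the primary result can be trusted when dropout is appreciable. The primary test itself is not in question.

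**Working it through.** **Inputs from the documents**

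- Test and level for the sample size: "With a one-sided continuity corrected chi-squared test at significance level 0.05" (SAP 5).
- Size and power: "data from 70 treated subjects per arm will provide at least 89% power to detect a 25% increase in the BICLA response rate", and "provide 74% power to detect 20% increase in the BICLA response rate" (SAP 5).
- Placebo rate: "assuming that the placebo arm has 25% response rate" (SAP 5).
- Allocation: "1:1:1:1:1 ratio in Part 1 of the study design" (SAP 2.2), so one placebo and four active arms.
- Primary test: "Chi-Square test, one sided p-value will be provided" (SAP Table 7.1-1).

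**Input not in the documents.** Other-reason dropout by arm is assumed, between 10% and 30%, with the same rate in all four active arms.

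**Step 1: the plan's own power.** The equivalent uncorrected size n solves (n/4)·(1 + √(1 + 4/(n·d)))² = 70, where d is the difference. This gives n = 62.2 for d = 0.25 and n = 60.4 for d = 0.20, with power of 90.0% and 75.0%. Exact binomial enumeration of the corrected test gives 89.8% and 74.7%. The stated 89% and 74% are reproduced.

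**Step 2: effect of deletion when leavers are true non-responders.** Let r be the response rate under the primary rule and q the proportion of other-reason leavers. Deletion leaves the responders unchanged and shrinks the denominator, so the observed rate is r/(1 − q). Take r = 0.25 in both arms, so there is no treatment difference under the primary rule.

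- Active, q = 0.20: 0.25/0.80 = 31.3%.
- Placebo, q = 0.10: 0.25/0.90 = 27.8%.
- Difference: +3.5 points.
- Pooled over five arms: (10 + 4 × 20)/5 = 18%, inside the trigger range.

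Rejection rates come from exact enumeration of the one-sided 0.05 test. Each arm has 70 subjects, a binomial number of leavers, and binomial responders among the rest. The uncorrected chi-square comes first, the corrected one in brackets. With everyone kept, the rejection rate is 5.2% (3.3%).

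| Leavers, placebo / active | Pooled | After deletion, placebo vs active | Difference (points) | Rejection |
|---|---|---|---|---|
| 17.5% / 17.5% | 17.5% | 30.3% vs 30.3% | 0 | 5.1% (3.3%) |
| 10% / 20% | 18% | 27.8% vs 31.3% | +3.5 | 11.1% (7.7%) |
| 10% / 25% | 22% | 27.8% vs 33.3% | +5.6 | 16.2% (11.7%) |
| 10% / 30% | 26% | 27.8% vs 35.7% | +7.9 | 23.1% (17.3%) |
| 20% / 10% | 12% | 31.3% vs 27.8% | −3.5 | 2.0% (1.2%) |
| 30% / 10% | 14% | 35.7% vs 27.8% | −7.9 | 0.6% (0.3%) |

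The last row has a 20-point imbalance between arms, yet (30 + 4 × 10)/5 = 14% does not reach the trigger.

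**Step 3: the opposite assumption.** Now let leaving be unrelated to response, with a true rate of 25% in both arms. Deletion gives 25% vs 25% and rejects at about 5%. The primary rule gives 0.25 × (1 − q):

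- 10% placebo / 20% active: 22.5% vs 20.0%, a difference of −2.5 points.
- 30% placebo / 10% active: 17.5% vs 22.5%, a difference of +5.0 points, with 18.9% rejection (uncorrected).

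**Step 4: what a tipping-point grid would show.** Suppose 18 of 70 respond in each arm, with 7 placebo and 14 active other-reason leavers. With all leavers as non-responders, the difference is 0. The extremes are −7/70 = −10 points (all placebo leavers respond, no active leavers do) and +14/70 = +20 points (all active leavers respond, no placebo leavers do). Reporting the whole grid tells the reader which assumptions would change the conclusion.

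**The case against.** The strongest objection is that Step 2 presupposes its answer: it makes every other-reason leaver a true non-responder, then counts the departure from the primary rule as bias. That is fair, and Step 3 shows the reverse case. The 3.5 points are conditional on leaving that is both unequal between arms and related to response. A reader might infer that the analysis manufactures a treatment effect where there is none. The documents do not support that as a general statement, because they give no dropout rates and do not say how leaving relates to response.

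A reader might also call this a complete-case analysis, say that it does not test the non-responder assumption, or call its result uninterpretable. These readings go too far. Subjects who left for LOE, AE or unknown reasons remain as failures, so the analysis is a limited alternative assumption and carries some information.

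Several features of the plan narrow the route to bias. Only subjects whose response is missing are deleted. SAP 8.1.1 makes anyone who fails a BICLA criterion, including the medication criterion, a non-responder, so some who left after disallowed treatment may already count as failures; the SAP does not spell this out. SAP 8.5 retains efficacy assessments made within 28 days of the last dose. Subjects and clinical assessors are blinded, which limits arm-dependent coding of reasons. Discontinuation reasons are tabulated by arm, so imbalance would be visible even if the trigger ignores it. The 3.5 points are also small beside the planned 90% interval, whose half-width at 25% response is 1.645 × √(2 × 0.25 × 0.75/70), about 12 points.

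Finally, a reader might infer that the sponsor could decide whether to run the analysis after seeing unblinded results. SAP 7.5.4 gives no timing, and a pooled percentage can be evaluated blind. The ambiguity of the range is on the page; the misuse is not.

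These points limit the size and likelihood of the bias. They leave standing the ambiguous, optional trigger and the absence, in the readable text, of a dropout analysis that keeps everyone.

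**Conclusion.** The point holds in a limited form. The only readable dropout sensitivity analysis for Day 169 BICLA is optional, has a trigger that is not a single number and is blind to imbalance between arms, and relaxes the non-responder assumption at one point by removing treated subjects.

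It is biased when other-reason leaving is both unequal and related to response. In the 10% / 20% case the size is +3.5 points, with uncorrected one-sided rejection of 11.1% against 5.2%; reversing the imbalance reverses the sign. When leaving is unrelated to response, the primary rule is the biased one if leaving is unequal. Neither single assumption can therefore show robustness.

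The figures rest on assumed dropout rates, 70 subjects per arm and 25% response. The primary test, its planned power and the sample size are not affected. This is an inexpensive improvement to a secondary check in a Phase 2 trial.

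**What to change.** In SAP 7.5.4, remove the 15-20% trigger and the optional wording. Specify that a tipping-point grid for Day 169 BICLA is always run on the full Efficacy Analysis Population for each active arm against placebo. The grid varies the number of responders among the other-reason leavers separately in each arm, from none (the primary rule) to all, and reports the difference, its 90% interval and the one-sided p-value in each cell.

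Multiple imputation from arm, randomisation strata and last observed component status may be added as one reference point on the grid; the grid does not depend on it. If the deletion analysis is kept, label it supplementary and state that it changes the analysed population.

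The cost is SAP wording and modest programming. The BICLA components are already collected at Days 29, 57, 85, 113, 141 and 169, so no visit, data item or sample size changes, and the primary analysis stays as it is.
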